#### **Test Algorithm**

Using the testing sample of subjects for whom medical records were acquired and redacted, PPV will be calculated by treatment group

**Abbreviations:** E+P HT, Estrogen and progestin hormone therapy; EC, endometrial cancer; HDVC, High-dose Premarin Vaginal Cream; LDVE, Low-dose vaginal estrogen; MDVE, Moderate-dose vaginal estrogen; PHI, protected health information; PPV, positive predictive value; QC, quality control; ICD-9-CM, International Classification of Diseases, Ninth Revision, Clinical Modification; ICD-10-CM, International Classification of Diseases, Tenth Revision, Clinical Modification.

# 4. ENDOMETRIAL CANCER CASE IDENTIFICATION

#### 4.1. Claims-Based Identification of Potential Endometrial Cancer Cases

Potential cases of endometrial cancer in the current study will be identified via a screening algorithm in each exposure and comparator cohort, i.e., LDVE, MDVE, HDVC, E+P HT, and non-users, using ICD-9 and ICD-10 codes. The screening algorithm will be defined as at least one ICD-9-CM or ICD-10-CM diagnosis code listed in Table 1 in any position (primary, secondary, etc.) and any location (outpatient, inpatient, ED, etc.) during the follow-up period. This algorithm was informed using preliminary case counts of patients in the HIRD with codes beginning with 182 and C54. Endometrial cancer is the most common cancer with codes starting with 182 or C54 and the vast majority of patients had either the code 182.0 or C54.1. The codes 182.8, C54.8 and C54.9 were also included to improve the capture of all possible cases of EC. Therefore, with this screening algorithm, an assumption is that all possible cases of EC have been captured. The index date of diagnosis will be the date of the first encounter with a diagnosis code in Table 1. Cases diagnosed during baseline will be considered prevalent cases and excluded from analysis.

	ICD-9-CM		ICD 10-CM
Code	Description	Code	Description
182.0	Corpus uteri, except isthmus [Endometrium] [Myometrium] [Fundus] [Cornu]	C54.1	Malignant neoplasm of endometrium
182.8	Other specified sites of body of uterus [Malignant neoplasm of contiguous or overlapping sites of body of uterus whose point of origin cannot be determined]	C54.8	Malignant neoplasm of overlapping sites of corpus uteri
N/A	N/A	C54.9	Malignant neoplasm of corpus uteri, unspecified

# 4.2. Identification of Validation Sample

Patients who meet the inclusion/exclusion criteria for the current study and fulfill the screening algorithm during follow up will qualify for inclusion in the validation study sampling. Table 2 will be populated with the counts of provisional cases identified with the screening algorithm. Preliminary feasibility counts for EC based on the screening algorithm show that approximately 500 cases are included across the vaginal estrogen exposure groups and approximately 100 cases in the E+P HT comparator group. The target number of cases to be sampled will be 300 across vaginal estrogen users (LDVE, MDVE, HDVC), all E+P HT, and 300 non-users. Cases will be sampled by exposure/comparator group, ICD code, and coding system, and/or visit type depending on case counts by subgroup (Table 2). Preference will be given to requesting medical records for provisional cases coding with ICD-10-CM codes because no validation study has been published for that coding system. If case counts are lower than expected, then medical records for all provisional cases will be sought. A yield of approximately 65% of requested medical records is expected and also that 10% of medical records returned will not be evaluable (e.g., missing data, wrong time period, etc.). Therefore, to obtain medical records for 300 provisional cases among vaginal estrogen users, records from all patients identified with the screening algorithm will be requested. A similar number of records will be requested from the non-user cohort.

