# 5.2. Medical Record Acquisition

For a sample of patients who meet the EC screening algorithm, at least one medical record per patient will be requested. To increase the likelihood that the medical record includes data required for adjudication, providers and/or facilities who have the patient's medical records based on the type of visit in claims will be ranked, such as:

- 1. Hospital or ED visit with EC; or
- 2. Physician office(s) with at least one claim for EC.

If no medical records can be obtained for a patient, an alternate patient will be selected from the list of eligible patients to meet the target number of medical records per subgroup for case validation. In addition, medical records obtained by the vendor that are missing key information, e.g., documentation from biopsy or pathology reports, will be considered non-evaluable. These patients will not count towards the target sample of 300 cases per exposure/comparator cohort, and records for an alternate patient will be requested.

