#### PFIZER CONFIDENTIAL

CT24-WI-GL02-RF023.0 Non-Interventional Study Protocol Template For Secondary Data Collection Study 20-May-2021

Characteristic	All provisional cases	Patients with retrieved medical records	Patients whose medical records could not be obtained	Patients in the training set	Patients in the testing set
Inpatient					
ED					
Other					
Reason medical record was not available					
[TBD]	N/A	N/A		N/A	N/A

**Abbreviations**: E+P HT, Estrogen and progestin hormone therapy; ED, emergency department; IUD, intrauterine device; N/A, not applicable; sd, standard deviation; TBD, to be determined.

The validation results will include true positive and false positive cases separately for the EC screening algorithm by exposure/comparator group (Table 4). The number of provisional cases, confirmed cases, not confirmed cases, non-evaluable cases, and PPV and 95% CI for each algorithm component will be calculated. The PPV will be calculated as the number of events confirmed as true cases via medical record review, divided by the total number of events that were evaluated for validation.

 $PPV = \frac{true \ positives}{true \ positives + false \ positives}$ 

The PPV will initially be evaluated for the broad EC screening algorithm for the full sample and by treatment group. Changes in PPV will be evaluated by shifting to more specific codes and counts of encounters. Sites of care will not be analyzed because preliminary case counts in the HIRD suggest that approximately 90% of subjects with an inpatient encounter also have an outpatient visit. In a sensitivity analysis, the non-evaluable cases will be added to both the numerator and denominator.

	Total Cases	Confirmed	Not Confirmed	Non- Evaluable	PPV
Algorithm Development	Ν	n (%)	n (%)	n (%)	% (95% CI)
Overall	Х	xx (xx.x)	xx (xx.x)	xx (xx.x)	xx (xx, xx)
Exposure Groups					
LDVE	Х	xx (xx.x)	xx (xx.x)	xx (xx.x)	xx (xx, xx)
MDVE	Х	xx (xx.x)	xx (xx.x)	xx (xx.x)	xx (xx, xx)
HDVC	Х	xx (xx.x)	xx (xx.x)	xx (xx.x)	xx (xx, xx)
Comparator Groups					
E+P HT	Х	xx (xx.x)	xx (xx.x)	xx (xx.x)	xx (xx, xx)
Non-users	Х	xx (xx.x)	xx (xx.x)	xx (xx.x)	xx (xx, xx)
ICD-9-CM					
182.0	Х	xx (xx.x)	xx (xx.x)	xx (xx.x)	xx (xx, xx)
182.8	Х	xx (xx.x)	xx (xx.x)	xx (xx.x)	xx (xx, xx)
ICD-10-CM					
C54.1	Х	xx (xx.x)	xx (xx.x)	xx (xx.x)	xx (xx, xx)
C54.8	Х	xx (xx.x)	xx (xx.x)	xx (xx.x)	xx (xx, xx)
C54.9	Х	xx (xx.x)	xx (xx.x)	xx (xx.x)	xx (xx, xx)
Number of separate					
encounters at any location					

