# 7.2. Development of the Algorithm

Based on the validation results in Table 4, separate algorithms for ICD-9-CM and ICD-10-CM coding systems will be developed because it is not certain that the crosswalk between ICD-9 to ICD-10 will yield an algorithm with comparable performance. The algorithms will be generated by choosing codes and the number of encounters that will maximize the detection of EC cases. For example, if Table 4 shows that there are true EC patients receiving the codes C54.8 or C54.9 then those codes will be included in the algorithm (Table 5). These algorithms will then be validated using the testing sample of provisional cases (Table 6). If there are enough cases in each exposure group (LDVE, MDVE, and HDVC) then the PPVs will be assessed by each vaginal estrogen treatment group and used to correct our estimates for measurement error. Otherwise, one PPV will be assessed for all three exposure groups. The PPVs for each treatment group will be used to correct estimates of association for measurement error in the main analysis. A sensitivity analysis will be conducted using the non-evaluable records. The PPVs for the final algorithm will be calculated assuming the non-evaluable records are cases and again assuming they are non-cases.

Algorithms assessed	Total Cases	Confirmed	Not Confirmed	Non- Evaluable	PPV
	Ν	n (%)	n (%)	n (%)	% (95% CI)
ICD-9-CM algorithm: [algorithm definition including ICD-9 EC codes and number of encounters]					
Overall	Х	xx (xx.x)	xx (xx.x)	xx (xx.x)	xx (xx, xx)
Exposure Groups					
LDVE	Х	xx (xx.x)	xx (xx.x)	xx (xx.x)	xx (xx, xx)
MDVE	Х	xx (xx.x)	xx (xx.x)	xx (xx.x)	xx (xx, xx)
HDVC	Х	xx (xx.x)	xx (xx.x)	xx (xx.x)	xx (xx, xx)
Comparator Groups					
E+P HT	Х	xx (xx.x)	xx (xx.x)	xx (xx.x)	xx (xx, xx)
Non-users	Х	xx (xx.x)	xx (xx.x)	xx (xx.x)	xx (xx, xx)
E+P HT	Х	xx (xx.x)	xx (xx.x)	xx (xx.x)	xx (xx, xx)
Non-users	Х	xx (xx.x)	xx (xx.x)	xx (xx.x)	xx (xx, xx)
ICD-10-CM algorithm: [algorithm definition including ICD-10 EC codes and number of encounters]					

 Table 5: Positive Predictive Values for Endometrial Cancer Algorithms by

 Exposure/comparator
 Group

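### The PPV sensitivity analyses reassign only non-evaluable records, about one sixth of the cases expected to lack an adjudicated status; unretrieved cases enter no PPV range

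*Protocol*

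**What the plan says.** Annex 2 is the protocol's plan for validating the claims algorithm for endometrial cancer in the HIRD. Section 4.2 reports preliminary counts from the screening algorithm: "approximately 500 cases are included across the vaginal estrogen exposure groups" and "approximately 100 cases in the E+P HT comparator group". It expects incomplete retrieval: "A yield of approximately 65% of requested medical records is expected and also that 10% of medical records returned will not be evaluable". To reach 300 records among vaginal estrogen users, every identified case is to be requested, and a similar number is to be requested among non-users.

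Section 5.2 provides for substitution: "If no medical records can be obtained for a patient, an alternate patient will be selected from the list of eligible patients". Records lacking key information are classed as non-evaluable and are also replaced. Section 6.4 makes non-evaluable an outcome of adjudication, and Table 3 has a separate column for patients whose records could not be obtained. The two categories are therefore distinct.

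Two PPV sensitivity analyses are specified. For the screening algorithm, section 7.1 says: "In a sensitivity analysis, the non-evaluable cases will be added to both the numerator and denominator". For the final algorithm, section 7.2 says: "The PPVs for the final algorithm will be calculated assuming the non-evaluable records are cases and again assuming they are non-cases". Section 7.2 also states that the group PPVs will correct the estimates of association in the main analysis.

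**The concern.** The plan accepts that a case of unknown status should be bounded by calling it a case and then a non-case. It applies that rule only to the smaller of two sources of unknown status. A woman whose record never arrives is as unknown as one whose record arrives incomplete, and the sampling rules in section 5.2 treat the two alike. The PPV bounds do not.

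The PPV is more than a descriptive figure here. If the correction multiplies each group's rate by its PPV, the usual form (the protocol gives no formula), the corrected hazard ratio (HR) is scaled by the ratio of the two group PPVs. Suppose retrieval is related to true case status, and differently so in the two groups. The error then passes into the corrected HR, and the reported PPV range would not show it. Retrieval by number of encounters is one plausible route, since section 5.2 seeks records from facilities and offices with an endometrial cancer claim and section 7.1 tabulates PPV by encounter count. The documents do not establish that this happens.

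**Working it through.** **Inputs.** From Annex 2, section 4.2: about 500 provisional cases among vaginal estrogen users, all requested; about 100 in the E+P HT group; 65% retrieved; 10% of returned records non-evaluable; target 300. From Annex 2, section 1: a PPV of 286/315 = 90.8% in the earlier validation study among E+P HT users, used here only as an illustration.

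**Reproducing the plan's figure.** Evaluable records = 500 × 0.65 × 0.90 = 292.5, against the target of 300. In reverse, 300/0.585 = 513 requests, against about 500. Both agree within 3%. Reading the 10% as a share of requested records would give 500 × (0.65 − 0.10) = 275, a poorer match, so the share of returned records is the right reading.

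**Cases without a status, per 500 requested.**
- Retrieved: 500 × 0.65 = 325
- Non-evaluable: 325 × 0.10 = 32.5
- Never retrieved: 500 − 325 = 175
- No status: 175 + 32.5 = 207.5, which is 41.5% of 500
- Share reached by the planned analyses: 32.5/207.5 = 15.7%, about one sixth

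For 100 E+P HT cases the share is the same: 6.5 of 41.5.

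**Width of the PPV range.** With PPV 0.908 among evaluable records, confirmed cases = 292.5 × 0.908 = 265.6.

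| Records reassigned | Lower | Upper | Width |
|---|---|---|---|
| Non-evaluable only (section 7.2) | 265.6/325 = 0.817 | (265.6 + 32.5)/325 = 0.917 | 10.0 points |
| All without a status, extreme bounds | 265.6/500 = 0.531 | (265.6 + 207.5)/500 = 0.946 | 41.5 points |
| All without a status, milder assumption | (265.6 + 175 × 0.708)/500 = 0.779 | (265.6 + 32.5 + 175 × 0.958)/500 = 0.931 | about 15 points |

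The first two widths are 32.5/325 and 207.5/500, so they do not depend on the PPV. The milder row assumes that unretrieved cases have a PPV from 20 points lower to 5 points higher than evaluable ones, with non-evaluable records at their extremes.

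**Effect on the corrected HR.** Let the two group PPVs move to opposite ends of their range. Their ratio then runs from 0.817/0.917 = 0.89 to 1.12 under the planned bounds, and from 0.531/0.946 = 0.56 to 1.78 under the extreme bounds for all cases without a status.

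**The case against.** The strongest objection is that 41.5 points is a limit and not an expectation. Its lower end requires every unretrieved woman with a qualifying code to be a non-case. Annex 2, section 4.1 says that endometrial cancer is the most common cancer under these codes, and the earlier PPV was 90.8%. This stands, so a reader should not infer that the true PPV range is four times the planned one. The milder comparison, 15 against 10 points, is the more realistic guide. Some moderate scenarios already fall inside the planned range: if all 207.5 unknown cases had a PPV of 0.70, the group PPV would be (265.6 + 145.3)/500 = 0.822, within 0.817 to 0.917.

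A reader might also infer a built-in imbalance, with vaginal estrogen users requested exhaustively and non-users replaced until a target is met. The documents do not support that. Section 4.2 requests a similar number of non-user records and states one yield for all groups. Taking alternates does not in itself change which women are retrievable, and a shortfall of equal proportion in both groups cancels in the corrected HR.

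Nor is it right that nothing planned looks at unobtained records. Table 3 compares them with retrieved cases on age, region, medications, facility type and reason for unavailability, and the example reasons in section 7.1 are administrative. The end of section 7.2 also promises sensitivity analyses for misclassification based on measures such as PPV. What remains is that Table 3 is descriptive, omits ICD code and encounter count, and feeds nothing into the PPV or the HR. The closing promise is general and sets no PPV for unretrieved cases.

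Finally, details may be left to the statistical analysis plan. But Annex 2 itself states what the PPV sensitivity analyses cover, so the point concerns a stated scope and not a missing detail.

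**Conclusion.** The point holds as one of scope. On the protocol's own yields, about 41.5% of requested provisional cases will have no adjudicated status, and the specified PPV sensitivity analyses reach about one sixth of them. Whether this causes bias is unknown. If retrieval is unrelated to case status, the PPV among evaluable records is unbiased. If it is related, the planned 10-point range understates the uncertainty: about 15 points under the milder assumption, and 41.5 points at the outer limit.

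The counts rest on the expected yields and on screening-algorithm cases. The final algorithm may require more encounters and so drop some single-code women, which would change the counts. The 90.8% comes from another population. This is a worthwhile, inexpensive improvement and not a demonstrated bias in the HIRD hazard ratios.

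**What to change.** In Annex 2, sections 7.1 and 7.2:

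- Extend the sensitivity analysis, by treatment group, to all requested cases meeting the final algorithm without an adjudicated status, whether unretrieved or non-evaluable. Keep a case in the count when an alternate replaces it.
- State a plausible range of PPV for unretrieved cases in advance, and report the all-case/all-non-case bounds as outer limits.
- Add a PPV weighted to all provisional cases of the group by the inverse probability of adjudication, modelled on claims variables known for everyone: ICD code, number of endometrial cancer encounters, visit type, age and calendar year.
- Carry both results to the corrected rates and hazard ratios.

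The cost is plan wording and some extra programming on claims data already held, with no further record requests. The reported PPV range will be wider.

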#### Table 2. Number of Provisional Endometrial Cancer Cases by Diagnosis Code, Exposure/comparator group, and Visit Type

			Number of Endometrial Cancer Cases							
	-			I	Exposure/Con	parator		Visit	Туре	
ICD Version	Code	Total	LDVE	MDVE	HDVC	Non-Users	E+P HT	Inpatient	Outpatient	
ICD-9-CM	182.0									
ICD-9-CM	182.8									
ICD-10-CM	C54.1									
ICD-10-CM	C54.8									
ICD-10-CM	C54.9									

# 5. MEDICAL RECORD ACQUISITION AND REDACTION

# 5.1. Vendor Identification and Contracting

HealthCore will contract with a vendor who has extensive training and experience in performing medical record acquisition and redaction. HealthCore contracts only with vendors who follow federal and state laws and regulations, including but not limited to privacy and security rules such as HIPAA.

# 5.2. Medical Record Acquisition

For a sample of patients who meet the EC screening algorithm, at least one medical record per patient will be requested. To increase the likelihood that the medical record includes data required for adjudication, providers and/or facilities who have the patient's medical records based on the type of visit in claims will be ranked, such as:

- 1. Hospital or ED visit with EC; or
- 2. Physician office(s) with at least one claim for EC.

If no medical records can be obtained for a patient, an alternate patient will be selected from the list of eligible patients to meet the target number of medical records per subgroup for case validation. In addition, medical records obtained by the vendor that are missing key information, e.g., documentation from biopsy or pathology reports, will be considered non-evaluable. These patients will not count towards the target sample of 300 cases per exposure/comparator cohort, and records for an alternate patient will be requested.

# 5.3. Electronic Copies of Medical Records

The vendor will provide HealthCore with scanned/electronic copies of the medical records that were successfully retrieved. They will also provide scanned/electronic copies with the PHI redacted.

# **5.4.** Quality Control

HealthCore will take steps to maximize the validity of the data obtained from the medical record review process. HealthCore will train the vendor responsible for acquiring the medical records to ensure standardization and consistency across time. Prior to initiating record acquisitions, HealthCore will hold a kick-off meeting/training session with the vendor to clarify any details related to record acquisition. Upon receipt of the copied and masked medical records, HealthCore will review each medical record to ensure completeness and the appropriate blinding of identifiable information. If any issues are identified in the review, the medical record will be returned to the vendor for correction and resubmission. Adjudicators will be blinded to exposure group, physician, and personal identification information.

# 6. EVENT ADJUDICATION

# 6.1. Endpoint Adjudication Committee

An Endpoint Adjudication Committee (EAC) comprising clinicians not employees of HealthCore or Pfizer will be formed to review the medical records and adjudicate the EC cases identified in the PFIZER CONFIDENTIAL

 $CT24-WI-GL02-RF02\,3.0\,\textit{Non-Interventional Study Protocol Template For Secondary Data Collection Study 20-CT24-WI-GL02-RF02\,3.0\,\textit{Non-Interventional Study Protocol Template For Secondary Data Collection Study 20-CT24-WI-GL02-RF02\,3.0\,\textit{Non-Interventional Study Protocol Template For Secondary Data Collection Study 20-CT24-WI-GL02-RF02\,3.0\,\textit{Non-Interventional Study Protocol Template For Secondary Data Collection Study 20-CT24-WI-GL02-RF02\,3.0\,\textit{Non-Interventional Study Protocol Template For Secondary Data Collection Study 20-CT24-WI-GL02-RF02\,3.0\,\textit{Non-Interventional Study Protocol Template For Secondary Data Collection Study 20-CT24-WI-GL02-RF02\,3.0\,\textit{Non-Interventional Study Protocol Template For Secondary Data Collection Study 20-CT24-WI-GL02-RF02\,3.0\,\textit{Non-Interventional Study Protocol Template For Secondary Data Collection Study 20-CT24-WI-GL02-RF02\,3.0\,\textit{Non-Interventional Study Protocol Template For Secondary Data Collection Study 20-CT24-WI-GL02-RF02\,3.0\,\textit{Non-Interventional Study Protocol Template For Secondary Data Collection Study 20-CT24-WI-GL02-RF02\,3.0\,\textit{Non-Interventional Study Protocol Template For Secondary Data Collection Study 20-CT24-WI-GL02-RF02\,3.0\,\textit{Non-Interventional Study Protocol Template For Secondary Data Collection Study 20-CT24-WI-GL02-RF02\,3.0\,\textit{Non-Interventional Study Protocol Template For Secondary Data Collection Study 20-CT24-WI-GL02-RF02\,3.0\,\textit{Non-Interventional Study Protocol Template For Secondary Data Collection Study 20-CT24-WI-GL02-RF02\,3.0\,\textit{Non-Interventional Study Protocol Template For Secondary Data Collection Study 20-CT24-WI-GL02-RF02\,3.0\,\textit{Non-Interventional Study Protocol Template For Secondary Data Collection Study 20-CT24-WI-GL02-RF02, Non-Interventional Study Protocol Template For Secondary Data Collection Study 20-CT24-WI-GL02-RF02, Non-Intervention Study 20-CT24-WI-GL02-RF02, Non$ 

May-2021 Page 63

claims. The EAC will comprise of two clinical experts with obstetrics and gynecology (OB/GYN) and/or oncology specialties (e.g., gynecologic oncologist).

The EAC will be identified prior to the initiation of medical record acquisition and adjudication. The members will provide clinical guidance to support finalization of the algorithm to identify EC. A training session will be provided to the EAC prior to initiation of adjudication. All members of the EAC must sign a conflict of interest form prior to this training. EAC members will also be required to disclose any conflicts of interest that arise during the course of the study.

The training session will include a review of the validation plan, as well as the policies and procedures for adjudicating the events. This training session will be a collaborative approach to illustrate the information that physician reviewers will use to determine EC events. After a thorough discussion has ensued, a document will be circulated among the study team and reviewing physicians to exemplify complete documentation of the EC adjudication process. Any changes made to the adjudication criteria or Clinical Review Form due to clarifications requested during the training session will be documented in an amendment to validation plan.

All members of the EAC are responsible for completing the following activities:

- Attend the training session prior to the initiation of adjudication.
- Understand the current case definition for the study endpoint to be adjudicated.
- Read and understand the contents of the validation plan and all future amendments to the validation plan.
- Complete the Clinical Review Form (Appendix A) for all events that require adjudication in the time frame specified in the consulting work order.
- Attend any scheduled conference calls or meetings for the final adjudication of events and the conduct of committee business, as needed.
- Participate in the orderly conduct of teleconferences and meetings (with technical assistance from HealthCore as needed).

